8.1.5 Record Retention

The investigator is responsible for retaining all essential documents listed in the ICH GCP Guideline. All essential documentation for all study subjects will be maintained by the investigators in a secure storage facility for a minimum of 3 years. The FDA requires study records to be retained for up to 2 years after marketing approval or disapproval (21 CFR 312.62), or until at least 2 years have elapsed since the formal discontinuation of clinical development of the investigational agent for a specific indication. These records will also be maintained in compliance with IRB, state and federal medical retention requirements, whichever is the longest. All stored records will be kept confidential to the extent required by federal, state, and local law. Destruction of research records will not proceed without permission of the IRB.

The FDA requires that the Investigator must retain study files for a period of at least 5 years after study completion or 2 years following the date that a marketing application is approved for the indication in which the study agent is being investigated (whichever is later).

9 REPORTING REQUIREMENTS

- Discuss all patients with CNMC Research Nurse
- Enter/Register all patients after calling Principal Investigator. The following forms should be completed:
 - Eligibility checklist
 - On study form
 - Drug Toxicity and/or Adverse Reactions
 - Adverse events will be collected as per SOPs (BMT_SOP003).
 - Serious adverse events will be collected and reported as per SOP (BMT_SOP004).

9.1 Adverse Event Reporting

Reporting of patient serious adverse events (SAEs) will be consistent with standard BMT SOP (BMT_SOP004_SAEReport). Unexpected, grades 4-5 AEs must be reported within 24 hours of knowledge of the event. Unexpected, grade 3 AEs must be reported within three business days of knowledge of the event. All other unanticipated problems will be reported to the IRB within seven (7) business days of knowledge of the problem. The Data Review Committee (DRC) Board will receive summary reports of all adverse experiences on at least an annual basis.

9.2 Reporting to the IRB

Following AEs should be considered as unanticipated problems that must be reported to the IRB within seven business days of the knowledge of the AE(s):

Single occurrence of a serious, unexpected, and uncommon event that is strongly associated with investigational products exposure

- A single or small number of a serious, unexpected event that is not commonly associated with investigational products exposure but is uncommon in the study population
- Multiple occurrences of an AE that, based on aggregate analysis, is determined to be an unanticipated problem. There should be a determination that the series of AEs represents a signal that the AEs were not just isolated occurrences and involve risk to human subjects
- An AE that is described in the investigator's brochure, protocol, or informed consent documents, but occurs at a specificity or severity that is inconsistent with prior observations
- A serious AE that is described in the investigator's brochure, protocol, or informed consent documents, but for which there is a clinically significant increase in the expected rate of occurrence
- Any other AE or safety finding, including those based on animal or epidemiologic data that would cause the sponsor to modify the investigator's brochure, protocol, or informed consent documents, or would prompt other action by the IRB to ensure the protection of human subjects

9.3 Pregnancy Reporting

Each pregnancy must be reported immediately (within 72 hours of identification) by reportable event submission system to the CNMC IRB. Subjects who become pregnant after Day 0 will be followed to term, and the following information will be gathered for outcome, date of delivery, health status of the mother and child including the child's gender, height and weight. Complications and or abnormalities should be reported including any premature terminations. A pregnancy is reported as an AE or SAE only when there is suspicion that the treatment may have interfered with the effectiveness of contraception or there was a serious complication in the pregnancy including a spontaneous abortion or an elective termination for medical rationale.

9.4 IND Annual Report to the FDA

The PI will be responsible for the preparation of a detailed annual synopsis of clinical activity, including adverse events, for submission to the sponsor. Each annual report

will summarize IND activity for 1 year beginning approximately 3 months before the IND FDA anniversary date. The sponsor's representative will notify the PI of the due date with sufficient time for the PI to assemble the required information.

9.5 Final Report

A report will be submitted to the FDA in accordance with ICH E3 Guideline "Structure and Content of Clinical Study Reports". A final report will also be submitted to the IRB at the time of study closure.

9.6 Reporting to the FDA

Serious adverse events (SAEs) that are unlisted/ unexpected, and at least possibly associated to the drug for this study should be reported promptly to the Food and Drug Administration (FDA). Fatal or life threatening SAEs that meet the criteria for reporting to the FDA must be reported to the FDA within 7 calendar days after awareness of the event by submitting FDA form 3500/MedWatch form. All other SAEs that meet the criteria for reporting to the FDA must be reported to the FDA within 15 calendar days after awareness of the event. A clear description of the suspected reaction should be provided along with an assessment as to whether the event is drug or disease related.

10 CLINICAL TRIAL OVERSIGHT AND MONITORING

This protocol will be conducted in accordance with the CNMC BMT Monitoring Plan. This protocol will be monitored in accordance with federal regulations and FDA guidance documents.

The conduct of this clinical trial will be evaluated in accordance with the CNMC BMT Quality Assurance Policy and Procedure Plan (SOP: BMT_SOP010_QA).

10.1 Safety monitoring

Safety monitoring will be conducted throughout the study; therefore safety concerns will be identified by continuous review of the data by the PI, clinic staff, and Data Review Committee (DRC).

10.2 Data Review Committee (DRC)

The Data Review Committee (DRC) is primarily being established to monitor serious adverse events which may occur during the trial, complete an annual review of the safety data, and to make any recommendations as appropriate. The DRC is required to review all unanticipated problems involving risk to subjects or others, SAEs, and all subject deaths associated with the protocol and provide an unbiased written report of

BMSCs

the event. The DRC should indicate concurrence or non-concurrence with the details of the report provided by the investigator. Reports for events determined by either the investigator or DRC to be related or unrelated to participation and reports of events resulting in death should be promptly forwarded to the IRBs.

Examination

Weight

0 = Weight gain or voluntary weight 5 = Involuntary weight stable, weight loss 1%-9% 10 = Weight loss \geq 10%

Height at Diagnosis

0 = < 1 channel decrease 5 = \geq 1, < 2 channel decrease 10 = > 2 channel decrease

Height at Follow-Up

0 = Height velocity \geq -1 SD 5 = Height velocity < -1 SD, > 2 SD 10 = height velocity \leq 2 SD

Abdomen

0 = No tenderness, no mass 5 = Tenderness or mass without tenderness 10 = tenderness, involuntary guarding, definite mass

Perirectal Disease

0 = None, asymptomatic tags 5 = 1-2 indolent fistula, scant drainage, 10 = Active fistula, drainage, No tenderness tenderness, or abscess

BMSCs

Extra-intestinal Manifestations

Fever ≥ 38.5 for more than 3 days in the past week, definite arthritis, uveitis, E. nodosum, P.gangrenosum

0 = None 5= 1

10= ≥ 2

12 APPENDIX 2:**12.1 PUCAI:**

Item	Points
1. Abdominal Pain	
No pain	0
Pain can be ignored	5
Pain cannot be ignored	10
2. Rectal Bleeding	
None	0
Small amount only, in <50% of stools	10
Small amount with most stools	20
Large amount (>50% of stool content)	30
3. Stool consistency of most stools	
Formed	0
Partially formed	5
Completely unformed	10
4. Number of stools per 24 hours	
0 to 2	0
3 to 5	5
6 to 8	10
>8	15

5. Nocturnal stools (any episode causing wakening)

No	0
Yes	10

6. Activity Level

No limitation of activity	0
Occasional limitation of activity	5
Severe restricted activity	10

13 APPENDIX 3:**13.1 CDAI**

Clinical or laboratory variable	Weighting factor
Number of liquid or soft stools each day for seven days	x 2
Abdominal pain (graded from 0-3 on severity) each day for seven days	x 5
General well being, subjectively assessed from 0 (well) to 4 (terrible) each day for seven days	x 7
Presence of complications	x 20
Taking Lomotil or opiates for diarrhea	x 30
Presence of an abdominal mass (0 as none, 2 as questionable, 5 as definite)	x 10
Hematocrit of <0.47 in men and <0.42 in women	x 6
Percentage deviation from standard weight	x 10

One point each is added for each set of complications:

- arthralgias or frank arthritis
- inflammation of the iris or uveitis
- presence of erythema nodosum, pyoderma gangrenosum, or aphthous ulcers
- anal fissures, fistulae, or abscesses
- other fistulae

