- Had bowel surgery other than perianal procedures (fistulotomy, seton placement, abscess drainage) within 3 months of enrollment.
- Has uveitis
- Has known pulmonary disease, excluding mild intermittent asthma

Primary Endpoints

- Safety and tolerability of the intravenous administration of human allogeneic bone marrow-derived MSCs to children and young adults with IBD, measured by the frequency of any SAEs, AEs and/or early treatment discontinuations.

Secondary Endpoints

- Magnitude of decrease in clinical index (for young adults we will use the CDAI and Mayo, and for children the PCDAI and PUCAI) relative to baseline, reporting the average decline and 95% confidence limit.
- Changes in biomarkers of inflammation and immunogenicity (i.e. C-reactive protein, fecal calprotectin, anti-HLA antibodies, viral-specific T cell activity)
- Where available, magnitude of endoscopic improvement, as assessed by change in endoscopic scores (Simple Endoscopic Score Crohn's Disease [SES-CD] for CD or Endoscopic Sub Score within the Mayo Score for UC) relative to baseline, reporting the average decline and 95% confidence intervals [3, 4].

Exploratory Endpoints

Blood, urine, saliva, and stool will be collected for evaluation of biomarkers

Accrual Period: Estimated accrual of 3-4 patients per year for 18-24 months

Study Duration: Approximately 48 months, including follow up

TABLE OF CONTENTS

1	BACKGROUND AND RATIONALE	8
1.1	Inflammatory Bowel Disease:	8
1.3	Description of the Study Agent/Intervention.....	9
1.4	Scientific Rationale and Clinical Justification	11
1.4.1	Rationale for the study of BMSCs in Pediatric IBD	11
1.4.2	PLAN OF STUDY:	13
1.4.3	Rationale for the Dosage and Treatment Period	14
2	STUDY OBJECTIVES AND DESIGN.....	15
2.1	Study Objectives:.....	15
2.1.1	Primary Objective:	15
2.1.2	Secondary objectives:	15
2.2	Study Design	15
2.2.1	Primary Endpoint	17
2.2.2	Secondary Endpoints	17
2.2.3	Exploratory Endpoint	17
2.3	Study Population.....	17
2.4	Recruitment Plan	18
2.5	Informed Consent.....	18
2.6	Eligibility criteria	19
2.6.1	Subject Inclusion Criteria	19
2.6.2	Subject Exclusion Criteria	19
3	Study Agent.....	20
3.1	Preparation Administration, and Dosage.....	20
3.2	Assessment of Subject Compliance	21
3.3	Concomitant Medications and Procedures.....	22
3.4	Prohibited Medications and Procedures	22
3.5	Study Schedule.....	22
3.6	Table 1: Protocol of Events.....	22
3.7	Baseline assessment/screening.....	25
3.8	Treatment Phase (Day 0, 7, 14, 21)	25

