This is a pilot phase 1 treatment protocol for subjects with moderate to severe CD or UC who have failed or are intolerant of one biologic. Subjects must have had a flexible sigmoidoscopy or colonoscopy or MR enterography within 2 months of enrollment, demonstrating active inflammatory bowel disease. Subjects with moderate to severe CD are defined differently in children and adults. In patients <17 years of age, moderate to severe CD will be defined as having a Pediatric Crohn Disease Activity Index (PCDAI) score of > 30 (range 0-100) and subjects with moderate to severe UC are defined as a patients with a Pediatric Ulcerative Colitis Activity Index (PUCAI) score of >34 (range 0-85). In patients \geq 18 years of age, moderate to severe CD will be defined as a CDAI of \geq 220 (range 0-600), and moderate to severe UC defined as a Mayo score of \geq 6 (range 0-12). In our study, at the specification of the FDA IND review, a young adult cohort will be enrolled first and monitored for toxicity. A pediatric cohort will only begin to enroll if there are no serious adverse events observed in the young adult cohort. Subjects will be closely monitored both by the study team to detect and evaluate adverse events (AEs), serious adverse events (SAEs), and toxicity requiring discontinuation of the intervention.

Three young adult patients (ages $17 \leq 22$ years) will be enrolled, staggered by at least 7 days. A fixed dose will be studied: 1×10^6 cells/kg administered intravenously (IV) weekly for 4 consecutive weeks. Infusions are administered over the first 28 days, followed by a 45 day monitoring period. Our chosen dose (1×10^6 cells/kg weekly for a duration of 4 weeks) is within the dosing parameters of previous trials. In trials of MSCs in pediatric GvHD, doses as high as 8×10^6 cells/kg/dose were given up to twice per week for four weeks. [51] The rate of administration (for patients < 35 kg, total infusion over 60 minutes, and for ≥ 35 kg, 4-6 ml/minute via infusion pump) is also consistent with prior pediatric administration in patients with GvHD. [51]

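### Appendix 3 scores weight deviation in the CDAI at 10 points per 1% with no direction, cap or definition of standard weight, so weight can meet the index cut-off and dominate its change from baseline

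*Protocol*

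**What the plan says.** Appendix 3 (13.1 CDAI) is a two-column table of items and weighting factors. The weight row reads "Percentage deviation from standard weight" and carries a factor of 10. The hematocrit row reads "Hematocrit of <0.47 in men and <0.42 in women" and carries a factor of 6. Neither row has a footnote, and no other section changes these factors.

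The index has two uses:

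- **Entry.** For patients of 18 years or more, section 1.4.2 states: "moderate to severe CD will be defined as a CDAI of \geq 220 (range 0-600". The Synopsis (Study Design) sets the same number as a strict inequality, above 220.
- **Secondary endpoint.** The Synopsis specifies change in clinical index from baseline, and "for young adults we will use the CDAI and Mayo, and for children the PCDAI and PUCAI". Section 2.2.2 asks for the average decline in CDAI with a 95% confidence limit. Table 1 in section 3.6 schedules disease activity assessment up to Day 720.

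The reference list gives sources for the PUCAI, PCDAI, SES-CD and Mayo score (references 1 to 4). None of the listed titles is a source for the CDAI, so Appendix 3 is the only scoring instruction a rater has.

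**The concern.** A factor of 10 on a percentage is large next to a cut-off of 220, and the row does not say which direction of deviation counts, where the contribution stops, or what standard weight is. A patient well away from standard weight could be classed as having moderate-to-severe Crohn's disease largely on weight. At follow-up, weight change from nutrition, fluid or corticosteroids (allowed within limits at entry) could appear as a large change in disease activity. If the row is read without a sign, weight regained beyond the standard would count as worsening.

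The hematocrit row raises a separate and smaller question. As worded, it asks whether a threshold is crossed, so the index would not distinguish mild from marked anaemia, although section 2.6.2 admits patients with hemoglobin down to 8 g/dL.

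**Working it through.** **Inputs, all from Appendix 3 unless noted**

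- Stools: "Number of liquid or soft stools each day for seven days", factor 2. One extra stool per day gives 1 × 7 × 2 = 14 points.
- Pain: "Abdominal pain (graded from 0-3 on severity) each day for seven days", factor 5. One grade on every day gives 1 × 7 × 5 = 35; the maximum is 3 × 7 × 5 = 105.
- Well-being: "General well being, subjectively assessed from 0 (well) to 4 (terrible) each day for seven days", factor 7. One grade on every day gives 1 × 7 × 7 = 49; the maximum is 4 × 7 × 7 = 196.
- Complications: five sets at 20 = 100. Antidiarrheal use: 30. Abdominal mass: 5 × 10 = 50.
- Hematocrit, read literally: 0 or 6.
- Weight: 10 points per 1% deviation.
- Cut-off: at least 220 (section 1.4.2) or above 220 (Synopsis).

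**Step 1: the protocol's own range of 0-600.** The capped items sum to 105 + 196 + 100 + 30 + 50 + 6 = 487. The stool and weight rows have no cap, so 600 is not a ceiling that the table produces, and the stated range cannot be reproduced from it.

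**Step 2: weight against the cut-off.** With every other item at zero:

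- 22% × 10 = 220, which meets the section 1.4.2 cut-off but not the Synopsis one.
- 22.1% × 10 = 221, which meets both.
- 10% gives 100, leaving 220 − 100 = 120 points to come from other items.
- 20% gives 200, leaving 20.

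**Step 3: weight against the change endpoint.** A change of 5 percentage points moves the score by 5 × 10 = 50, compared with 35 for a full grade of pain all week, 49 for a full grade of well-being all week, and 14 for one stool per day. In kilograms, assuming a standard weight of 50 to 70 kg:

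| Weight change | Standard weight 70 kg | Standard weight 50 kg |
|---|---|---|
| 3 kg | 3/70 × 1000 = 43 points | 3/50 × 1000 = 60 points |
| 5 kg | 5/70 × 1000 = 71 points | 5/50 × 1000 = 100 points |

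If all three young adults had Crohn's disease, one 50-point weight shift would move the cohort mean by 50/3, about 17 points. With fewer such patients it would move the mean more.

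**Step 4: comparison inside the protocol.** The PCDAI weight item in Appendix 1 scores weight gain 0, counts loss in two steps and stops at 10 points. The two indices are on different scales, so points should not be compared directly. The difference in form is what matters: the pediatric item has a direction and a ceiling, and the CDAI row has neither.

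**Step 5: hematocrit.** Read literally, a man at 0.46 and a man at 0.27 both score 6. If the row were instead meant per percentage point below 47 (men) or 42 (women), which is an assumption, a hematocrit of 30% would score 6 × 17 = 102 in a man or 6 × 12 = 72 in a woman. The two readings differ widely, and the appendix does not say which applies.

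**The case against.** Much can be said on the other side, and most of it narrows the point.

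- **Weight alone does not admit a patient.** Section 2.6.1 also requires active disease on endoscopy or MR enterography within two months, and failure or intolerance of biologic therapy. That inclusion criterion points to section 2.3, which names only the PCDAI and PUCAI; the CDAI cut-off enters through the Synopsis and section 1.4.2. This stands. The claim concerns the index cut-off, not full eligibility.
- **The table never says absolute deviation.** A deviation can carry a sign, so equal scores for over- and underweight patients are one reading of a silent row. This stands, and is why the defect is stated as a missing convention.
- **The 0-600 range.** A reader might infer that this range proves the weight factor wrong, since 487 plus 11.3% × 10 already reaches 600. It does not: nine stools a day add 9 × 14 = 126, and 487 + 126 = 613 with no weight points.
- **Eligible as printed, ineligible if corrected.** A reader might take four stools a day (56), one grade each of pain (35) and well-being (49), and the hematocrit 6, for a total of 146. Adding 10% weight deviation gives 246 at factor 10, or 156 at an assumed factor of 1. That contrast changes only one of the two doubtful rows. If hematocrit is also scored per point, the sum is 56 + 35 + 49 + 10 = 150, and a 12-point shortfall adds 72, giving 222. The flip is not established for an anaemic patient.
- **Hematocrit as a cause.** Compared with a per-point reading, scoring it as 0 or 6 lowers the total for patients more than one point below the reference. It does not help weight reach 220, so it is a separate matter. The row could also be read as naming reference values, and change in anaemia remains visible outside the index because Table 1 schedules blood counts from screening to Day 73.
- **The right factor.** The documents contain no source for the CDAI, so they cannot show that 10 is a misprint or what should replace it.

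None of this supplies the missing direction, cap or definition, or alters the 22% and 50-point results.

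**Conclusion.** The point holds in limited form. A rater who follows Appendix 3 literally gives 10 points per 1% of weight deviation: 22% meets the section 1.4.2 cut-off with nothing else scored, and 5 percentage points of weight change outweigh a full grade of pain or well-being on every day of the week. That can distort an entry measure and a secondary endpoint. The hematocrit row is a second, smaller ambiguity.

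The entry result needs only the printed factors and cut-off; the kilogram figures assume a standard weight of 50 to 70 kg. The documents do not establish the correct factor, an intended absolute value, or the wrongful admission of any patient.

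The scope is Crohn's patients aged 18 or over within a cohort of three, taking the Synopsis age split that puts younger patients on the pediatric indices. The primary safety endpoint, the stopping rules in section 7.1.4 and the worsening criterion in section 6 (PCDAI and PUCAI) do not use the CDAI. The appendix should be corrected, but the issue ranks below must-fix.

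**What to change.** 1. Check the weight and hematocrit rows of Appendix 3 against the source CDAI, cite that source in the reference list, and correct the weight factor if it differs.
2. State the sign convention for weight deviation, any cap, and how standard weight is determined.
3. State how hematocrit is scored: as a threshold, or as a shortfall from a sex-specific reference.
4. Make the cut-off the same in the Synopsis and section 1.4.2, since exactly 220 passes one and fails the other.
5. Re-score, at entry and follow-up, any Crohn's patient aged 18 or over already scored with the printed table.

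The cost is one corrected appendix and score sheet, and re-scoring of at most three patients from data already collected. Scheduled blood counts cover hematocrit from screening to Day 73. Table 1 schedules none at Days 180, 360 and 720, so re-scoring that row at those visits depends on what was recorded.

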14 APPENDIX 4:**14.1 MAYO SCORE**

Endoscopic findings	Normal, inactive disease	0
	Mild disease, erythema, decreased vascular pattern, mild friability	1
	Moderate disease, marked erythema, absent vascular pattern, erosions, friability	2
	Severe disease, spontaneous bleeding	3
Stool frequency	Normal for the patient	0
	1-2 more than normal	1
	3-4 more than normal	2
	5 or more stools than normal	3
Rectal bleeding	No blood seen	0
	Streaks of blood with stool less than half the time	1
	Obvious blood with stool most of the time	2
	Blood alone passed	3
Physician's Global Assessment		
	Normal	0
	Mild disease	1
	Moderate disease	2
	Severe disease	3

